**b. Inclusion/Exclusion Criteria:**

1. PLHIV (for medical file review)

Inclusion:

- Adult individuals, 18 years of age or older
- Active in care (i.e., not in default)
- Receiving HIV care and treatment at one of the four study sites.

2. PLHIV (for survey participation)

Inclusion:

- Adult individuals, 18 years of age or older
- Active in care (i.e., not in default)
- Receiving HIV care and treatment at one of the four study sites.
- Sought care at health facility on the day of survey data collection

Exclusion (for survey participation only):

- Any clinical or mental condition (for example, but not limited to: patients with delusions, hallucinations, impaired cognitive function, mental retardation, medical condition with physical deterioration, or under the influence of drugs or alcohol at the time of study recruitment), that as per the investigator's opinion/assessment, would preclude provision of informed consent or make study participation unsafe or unethical;
- Being at the health facility for reasons other than their own medical appointment and/or picking up their own medication;
- Those who do not have routine care at the selected health facility (e.g., individuals who receive HIV care and treatment at a different facility than their own due to stigma or other reasons).

3. Health Care Workers

Inclusion:

- Adult individuals, 18 years of age or older;
- working as physicians, nurses, medical technicians, health counselors, community health care workers, or other clinical and non-clinical staff (e.g.,

receptionists, data entry clerk) who provide health services to adults living with HIV at one of the four study sites;

- willing to be followed as a study participant during the 6-month study period, and does not intend to transfer to another HF during the study period (per investigator's assessment at time of recruitment), as self-reported.
- Be able to read and write in Portuguese, as self-reported.

Exclusion:

- Those who are not permanent members of the health facility staff (i.e., floating providers that work at multiple sites in a given week);
- Any clinical or mental condition, including influence of drugs or alcohol at the time of study recruitment, that as per the investigator's opinion/assessment, would preclude provision of informed consent or make study participation unsafe or unethical;

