People living with HIV (survey): The study team will recruit participants to complete the baseline and endline surveys at the time the individuals are leaving an appointment for HIV care at one of four eligible health care facilities. Recruitment will be done using convenience sampling when the individual exits the health facility after receiving care. If the individual is interested in participating in the study, a study assistant will bring them into a private room to discuss their eligibility and study procedures (complete surveys at study baseline or endline, i.e., 6 months after the study begins, and to the use of a subset of data from their medical records regarding ART medication pick-up history within the previous 6 months). If eligible and they agree to participate, their informed consent will be obtained by the study assistant at the health facility. Participants can withdraw at any time without impact on the clinical care they are receiving.

People living with HIV who are followed as part of routine care (estimated n=16,000): The study team will not formally recruit and consent these individuals to participate in the study, as only a chart review will be performed. For the inclusion of these individuals' data, we will seek a waiver of informed consent, to be developed and included in the submission to the ethics committees/Institutional Review Board (IRB), to access their retention data and viral load results over the course of the study.

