#### **Objective 2:**

With Objective 2 most of our outcomes are continuous measurements, and analyses will be similar to those described above: linear mixed effects models that take advantage of the factorial nature of outcome, with clusters defined as study sites, and unadjusted and adjusted for a small number of PLHIV-level covariates (age, sex, educational level, marital status, language, duration on ART, and history of ART medication pick-ups within the previous 6 months). For binary outcomes (e.g., undetectable viral load), we will fit generalized linear mixed effects models with a logit link function.

Every patient is given 30, 60, 90, or 180 days to pick up their ART medication, as indicated in the medical charts. If a patient picks up medication after the indicated/scheduled date, they will be considered "non-adherent" for each day after their specific pick-up date; this will be assessed over the course of the 6-month follow-up and will be treated as a continuous variable (a proportion between 0 and 1 for each participant). Participants who are lost to follow-up from the health facility during the 6-month follow-up period will be considered "non-adherent" for the days that they are lost. For persons who die or are known to have transferred care outside of the catchment area, the proportion of time on medication will be computed using only time prior to death or transfer of care. For our primary retention outcome (proportion of time on medication), normality assumptions are unlikely to hold, perhaps even after data transformation. Hence, we will fit a cumulative probability model (CPM) with fixed effects for the clinics. The CPM is well-suited for this setting because it does not require symmetry/normality in the outcome (which is bounded between 0 and 1 and likely not normal); in the absence of covariates, it reduces to the Wilcoxon rank sum test. The CPM has been shown to perform well in settings investigating medication adherence. Specifically, the distribution of the proportion of time on medication will be modeled as

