## Appendix 10: Clinical data to be extracted from EPTS for only the PLHIV participating in the survey (Objective 2)

1. Patient ID
2. Date of enrollment in HIV services
3. ART initiation date
4. ART pick up dates (all in previous 6 months)
5. Scheduled ART pick up dates (all in previous 6 months)
6. Differentiated model of care (all in previous 6 months)
7. Viral Load test results and dates (all in previous 6 months)
8. Type of drug dispensation (all documented in previous 6 months)

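### Adjusted models for endline patient-survey outcomes control for a pick-up history measured 83–100% after study start, so the adjusted coefficient may not be the total intervention effect

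*Combined protocol and SAP*

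**What the plan says.** Section 10, Objective 2, plans linear mixed models, unadjusted and adjusted for patient-level covariates. The list ends with "history of ART medication pick-ups within the previous 6 months". No index date is given. The covariates for Objective 1 and for the primary cumulative probability model (CPM) are both described as baseline; this list is not. The list includes language, which the patient survey collects (Appendix 2) and the routine extraction (Appendix 9) does not, so it fits the survey models.

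Other sections point to the survey date as the anchor:

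- Section 7e: survey participants agree "to the use of a subset of data from their medical records regarding ART medication pick-up history within the previous 6 months".
- Section 8a: the past six months of pick-up history are collected for analysing the survey data. Endline is 6–7 months after study initiation, and the two waves may include different patients.
- Appendix 10: the extraction for survey participants includes "Scheduled ART pick up dates (all in previous 6 months", alongside the actual pick-up dates.

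The Timeline places the surveys in Months 1–2 and 6–7 and the training sessions in Months 1–4. Hypothesis 2 expects higher medication adherence and higher satisfaction at 6 months at the site receiving both trainings.

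**The concern.** Adjusting for a variable measured after randomisation changes what the treatment coefficient estimates if the intervention can move that variable, directly or through the outcome. Section 4 describes one such route: patients who perceive negative attitudes in their clinicians are less likely to adhere. The inputs also match the trial's own adherence outcome, which counts days of non-adherence "If a patient picks up medication after the indicated/scheduled date"; "this will be assessed over the course of the 6-month follow-up". Appendix 10 supplies the same two kinds of date.

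The models at stake are those for satisfaction, medical mistrust and perceived provider stigma at endline. A gap between their adjusted and unadjusted results could be read as confounding removed when it is really part of the effect being conditioned away.

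**Working it through.** **1. The plan's own figures.** Section 7c gives detectable differences of 0.55, 0.71 and 0.96 SD for survey outcomes at ICC 0.025, 0.05 and 0.10 (80 surveys per facility, about 80% power, two-sided 0.05). Section 10 compares two sites with two. Effective n per group = 2×80 / [1 + 79×ICC] = 53.8, 32.3 and 18.0. A two-sample noncentral t on these gives 0.545, 0.708 and 0.962 SD. The figures reproduce and do not depend on this covariate.

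**2. Timing.** With the survey at t elapsed months, the look-back runs from t−6 to t, and the share after study start is min(t, 6)/6. Month 1 is taken to begin at time 0.

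| Survey | Window (months) | Share after start |
|---|---|---|
| Endline, first day of Month 6 (t = 5) | −1 to 5 | 5/6 = 83% |
| Endline, t = 6 | 0 to 6 | 100% |
| Endline, t = 7 | 1 to 7 | 100% |
| Baseline, t = 0 | −6 to 0 | 0% |
| Baseline, t = 2 | −4 to 2 | 2/6 = 33% |

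The endline window covers 75–100% of training Months 1–4. One variable name therefore means a mostly pre-start quantity at baseline and a mostly or wholly post-start one at endline.

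**3. Is a pre-start value available?** Appendix 10 reaches back six months from the survey. Appendix 9 lists pick-ups during the study period. A patient surveyed only at endline therefore has at most one pre-start month of six (at t = 5) and never a full pre-start window.

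**4. What the variable might measure.** The plan does not say. "Every patient is given 30, 60, 90, or 180 days to pick up their ART medication", so a simple count over 180 days would be about 180/30 = 6, 180/60 = 3, 180/90 = 2 or 180/180 = 1, and would mostly track the dispensing schedule. A timeliness measure would resemble the adherence outcome. If that outcome's follow-up runs from 0 to 6 months (assumed), the two windows overlap by 83–100%.

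**5. Possible size.** The documents give no correlations, so these are illustrations that treat endline as a single cross-section.

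- *Pick-ups respond only to the outcome.* With unit within-arm variances and within-arm correlation r, the arm difference in pick-ups is r×d, and the adjusted effect is d − r(r×d) = d(1 − r²). For d = 0.55 SD: r = 0.1 gives 0.55×0.99 = 0.544; r = 0.3 gives 0.55×0.91 = 0.501; r = 0.5 gives 0.55×0.75 = 0.413. The losses are 1%, 9% and 25%.
- *Training changes pick-ups (a), which change the outcome (b), with a direct effect of 0.30 SD.* The total is 0.30 + ab. At a = b = 0.2 the total is 0.34 and the adjusted estimate 0.30; at a = b = 0.4 they are 0.46 and 0.30. With an assumed common cause of pick-ups and outcome (loading 0.5 on each), the adjusted estimate is 0.30 − 0.25a, that is 0.25 and 0.20, so it is not a clean direct effect either.
- *Pick-ups do not differ by arm.* There is no distortion.

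**6. Precision lost by omitting it.** For two sites against two, the variance is ICC + (1−ICC)/80. At ICC 0.025 this is 0.025 + 0.0122 = 0.0372, so the SE is 0.193 SD. If the covariate explains only within-site variance, the ratio of SE without it to SE with it is √{[ICC + (1−ICC)/80] / [ICC + (1−ICC)(1−r²)/80]}. For r = 0.1, 0.3 and 0.5 the SE rises by 0.2%, 1.5% and 4.4% at ICC 0.025, and by 0.05%, 0.5% and 1.3% at ICC 0.10.

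**The case against.** The strongest reply is that bias needs several conditions, none of which the plan establishes: the variable must reflect adherence, training or the outcome must move it among those surveyed, and it must relate to the outcome. The sample works against the second condition. Respondents must be "Active in care (i.e., not in default", and "Recruitment will be done using convenience sampling when the individual exits the health facility after receiving care"; both probably narrow arm differences in pick-ups. After study start is also not after training: if sessions end at 4 elapsed months, only 17–50% of the look-back follows the last one. Even the largest illustrated shift, 0.1375 SD, is 0.1375/0.193 = 0.71 of a standard error. All of this stands, and it is why the point is conditional and carries low weight.

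It can also be said that the Objective 2 analyses are described as similar to those of Objective 1, whose covariates are baseline. That reading is possible, but the listed data cannot deliver it for patients surveyed only at endline.

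Adjusting for visit history has a rationale under convenience sampling on exit. The covariate might also explain between-site differences, which the precision formula excludes. Both are fair costs of omission. How the two survey waves enter one model is not stated either, and the covariate's role could differ in a combined model.

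A reader might infer that the trial's adherence result is compromised. The documents do not support that: the primary CPM uses baseline covariates, and unadjusted mixed models are reported throughout. For mixed models of the routine cohort, the window is merely undefined.

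**Conclusion.** The concern holds in conditional form. On the survey-anchored reading, the covariate is measured 83–100% after study start at endline, with 83% reached only on the first day of Month 6. Following the plan would then condition the adjusted satisfaction, mistrust and stigma models on a post-randomisation variable. Whether this distorts the coefficient depends on how the variable is built and on effects that the documents do not quantify, so size and direction are unknown. The 1%, 9% and 25% losses rest on assumed correlations.

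Two stronger inferences are tempting and unsupported. One is that the adjusted estimates are biased; they are not if pick-ups do not differ by arm. The other is that endline-only respondents have no pre-study pick-up data; a survey early in Month 6 would reach back up to one month before start. What they lack is a full pre-start window.

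Weight is low: Section 7c calls the survey exploratory, and Section 12 presents the four-site trial as informing a later, fully powered one. The change is still worth making, because satisfaction is named in Hypothesis 2 and the remedy is cheap.

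**What to change.** In Section 10, Objective 2, state that the main adjusted models for endline survey outcomes (satisfaction, medical mistrust, perceived provider stigma) omit pick-up history over the previous six months and keep the other listed covariates. State also that any model retaining it is a secondary analysis conditional on post-start pick-ups, and define the variable there as a count or as timeliness.

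This needs no new data. It costs an SE increase of about 0.2–4.4% at ICC 0.025 for assumed r of 0.1–0.5, if the covariate explains only within-site variance, and it gives up some adjustment for visit history under exit convenience sampling.

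An optional alternative is to define the covariate over the six months before a fixed study start date. That would need a wider extraction than the appendices list and might need further ethics approval. It would also give no value for patients new to ART.

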**c. Calculations of Sample Size:**

**Objective 1:** Each of the four selected sites have no more than 25 health care workers providing HIV care, so we anticipate a maximum total of 100 health care workers equally divided between each intervention arm and the control arm. With  $n=25$  in all arms, assuming an intraclass correlation coefficient (ICC)=0.10, and two-sided type I error rate of 0.05, then we anticipate that we will have approximately 80% power to detect a difference of 1.07 standard deviations of the outcome (e.g., change in resilience score between baseline and after intervention), or the change in stigma score between baseline and after intervention) between the intervention vs. control for each of the two interventions. If ICC=0.05 (or 0.15), then we will have approximately 80% power to detect a difference of 0.85 (or 1.26) standard deviations.

For our qualitative interviews, we will continue to collect data until we have reached data saturation. Based on similar interviews conducted in 2022 (unpublished, IRB# 99/CIBS-Z/22), we believe we will reach saturation with no more than 40 interviews.

**Objective 2:** Each of the four health facility sites serve at least 4,000 patients enrolled on ART who will be scheduled for clinic visit(s) during the study period. With a minimum of  $n=4,000$  in each facility, assuming an ICC=0.05, and two-sided type I error rate of 0.05, then we anticipate that we will have approximately 80% power to detect a difference of 0.64 standard deviations of the outcome (e.g., proportion of time on medication) between the intervention vs. control. If ICC=0.025 (or 0.10), then we will have approximately 80% power to detect a difference of 0.45 (or 0.91) standard deviations.

The survey will be done in a sub-population of the cohort of HIV-positive patients at all four sites. Due to the exploratory nature, sample sizes for the patient surveys were not calculated based on existing assumptions. We estimate that 80 surveys per HF ( $n=320$ ) will provide us with the requisite baseline preliminary data on how they experience health care. For outcome

measures available on only these surveyed participants, we anticipate approximately 80% power to detect differences of 0.55, 0.71, and 0.96 standard deviations of the outcome assuming ICC of 0.025, 0.05, and 0.10, respectively.

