## **Data Analysis**

### **Objective 1:**

#### Quantitative Data Analysis

We will first conduct descriptive analyses. Our psychological and psychosocial measures are continuous or pseudo-continuous (e.g., sums of Likert-style questions) variables. Our outcomes

will be changes in psychosocial measures from baseline to follow-up. Descriptive analyses will include boxplots and summary measures by intervention arm (4 groups). Our formal analyses (those that test hypotheses) will take advantage of the factorial nature of this pilot cluster randomized control trial. These analyses will group together sites as receiving resilience intervention (yes vs. no) and receiving anti-stigma intervention (yes vs. no); therefore, results from two sites will be compared with results from two other sites. This gives us a larger sample size for each comparison and allows us to fit linear mixed effects models that include random effects to account for the correlation between measurements taken from participants at the same site while ensuring that the fixed effect of the intervention is identifiable. We will report results from models that are unadjusted and adjusted for a small number of HCW-level baseline covariates (age, sex, HCW role, and baseline measures of the outcome). Model diagnostics will be performed and outcome variables will be transformed, if necessary, to meet model assumptions.

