$\text{logit}(P(Y \leq y)) = \beta_0(y) + \beta_1 \text{Intervention} + \beta_s \text{site} + \beta_x X$ , where  $\beta_1$  is the effect of the intervention on the log-odds ratio scale. Our primary objective is to test the null hypothesis,  $H_0: \beta_1 = 0$ . We will provide estimates of  $\beta_1$ , 95% Wald confidence intervals, and two-sided p-values. As with our other analyses, we will take advantage of the factorial nature of the model by grouping interventions as receiving resilience intervention (yes vs. no) and receiving anti-stigma intervention (yes vs. no). An interaction between the two interventions will also be assessed to see, for example, if the interventions are synergistic. The primary model will be adjusted for study site to acknowledge similarities between patients at the same site, and it will also be adjusted for a small number of patient-level baseline covariates, that are usually predictive of adherence to medications (e.g., age, sex, and education). In the model with the interaction between two interventions, study site will not be included so that the interaction effects are identifiable. In additional crude secondary analyses, we will investigate how changes in HCW measures correlate with patient outcomes by including average HCW metrics in models, replacing study site with this continuous variable. These latter analyses will be very much exploratory, as with only four study sites, we will have limited information to estimate these associations.

We will also compute three secondary measures of patient retention:

- (1) Monthly medication pick-up. Specifically, measured from the first day of ART initiation, any ART medication pick-up between days 16 and 45 will count as medication pick-up during month 1, any medication pick-up between days 46 and 75 will count as medication pick-up during month 2, and so forth, up until 6 months (i.e., medication pick-up between day 346 and 375); if the patient was enrolled on a three month pick up we will calculate on time pickups using the mark 15 days before and 15 days after the scheduled visit.

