## Appendix 9: Routinely collected clinical data of all PLHIV to be extracted from EPTS (Objective 2)

1. Age
2. Sex
3. Date of HIV diagnosis
4. Education level (highest completed)
5. Marital status
6. Number of children alive
7. HIV status disclosed to family (yes/no)
8. ART initiation date
9. ART pick up dates (all during study period)
10. Scheduled ART pick up dates (all during study period)
11. Clinical appointment dates (all during study period)
12. Scheduled clinical appointment dates (all during study period)
13. Viral Load test results and dates (all during study period)
14. Pregnancy status at time of study.
15. Differentiated model of care (all documented during study period)
16. Type of drug dispensation (all documented during study period)
17. Blood pressure (all results during study period)
18. Weight (all results during study period)
19. Height
20. TB treatment
21. WHO staging
22. patient ID
23. CD4 results and dates (all during study period)

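### Dispensing interval strongly predicts the primary adherence outcome but is not a named covariate; the starting interval should be pre-specified in the cumulative probability model

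*Combined protocol and SAP*

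**What the plan says.** Section 10, Objective 2, defines proportion of time on medication over 6 months. It says "Every patient is given 30, 60, 90, or 180 days to pick up their ART medication". Each day beyond the scheduled date until pick-up counts as non-adherent, and so do days lost to follow-up.

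The outcome is analysed with a cumulative probability model (CPM) with fixed clinic effects. The primary model is to be "adjusted for a small number of patient-level baseline covariates, that are usually predictive of adherence to medications", with age, sex and education as examples. A longer covariate list for the Objective 2 mixed models adds marital status, language, duration on ART and pick-up history over the preceding 6 months. Neither list names dispensing interval or care model. The model with the interaction between the two trainings leaves study site out, so that its effects can be estimated.

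For the whole cohort, Appendix 9 extracts pick-up dates, scheduled dates, care model and "Type of drug dispensation (all documented during study period"). Pick-up dates from the preceding 6 months appear only in Appendix 10, which covers survey participants. Pick-up schedules are treated separately only in the secondary retention measures (the three-month rule in measure 1, and 3a against 3b).

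**The concern.** Lateness can be recorded only when a pick-up falls due. Two patients who are equally likely to be late at each pick-up, by the same number of days, get different outcome distributions if one collects monthly and the other every six months. Interval is thus a strong predictor that the plan does not commit to using.

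Two things are at stake. Within sites, leaving it out adds avoidable variance. Between sites, there is one facility per arm, and for each training "results from two sites will be compared with results from two other sites", so randomisation cannot be relied on to balance the dispensing mix. Where the model does not contain a full set of site terms, a difference in mix enters the training contrast in either direction.

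**Working it through.** **The plan's own figure.** "Each of the four health facility sites serve at least 4,000 patients enrolled on ART", and the plan claims "80% power to detect a difference of 0.64 standard deviations of the outcome" at ICC 0.05, two-sided 0.05. With two sites against two, the effective n per group is 2m/(1+(m−1)ICC) = 8,000/(1+3,999×0.05) = 39.8. A two-sample t-test with 2×39.8−2 = 77.6 df gives 0.636 SD. At ICC 0.025 and 0.10 the results are 0.448 and 0.910 SD, against 0.45 and 0.91 stated. The plan's figures reproduce.

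**Opportunities to be late (definition only).** Scheduled dates in 180 days = 180/interval, that is 6, 3, 2 and 1 for 30, 60, 90 and 180 days. With pick-up dates spread evenly, the first falls on average at interval/2 = 15, 30, 45 and 90 days. On average 8%, 17%, 25% and 50% of the window therefore cannot be scored non-adherent, even for a patient who never returns.

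**Share at exactly 1.** If each pick-up is late with probability p and nobody is lost, the share is (1−p)^k with k = 6, 3, 2, 1. The length of the delay does not matter.

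| p (assumed) | 30 d | 60 d | 90 d | 180 d |
|---|---|---|---|---|
| 0.1 | 53% | 73% | 81% | 90% |
| 0.2 | 26% | 51% | 64% | 80% |
| 0.5 | 1.6% | 12.5% | 25% | 50% |

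**Site means.** These were simulated with a uniform first date, exponential delay and the same lateness at every interval. The shift is 0.10 × (mean at 180 days − mean at 30 days).

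- 10% late, mean 7 days, no loss: about 0.2 points.
- 20% late, mean 14 days, no loss: gap 0.066, so 0.7 points.
- 50% late, mean 20 days, no loss: 0.951 − 0.766 = 0.185, so 1.8 points.
- 10% to 40% late, mean 7 to 14 days, with 6.7% lost over 6 months: gap 0.036 to 0.132, so 0.4 to 1.3 points. The 6.7% is 1−√0.87, from the 87% 12-month retention in the Introduction, assuming a constant hazard.
- Delay proportional to interval, same losses: gap 0.023 to 0.056. The share at 1 still differs, for example 25% against 78%.

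**Effect on a CPM-type contrast without site terms.** The setting was no training effect, 8,000 against 8,000 patients, an assumed reference mix of 40/10/35/15% on 30/60/90/180 days, 6.7% loss, and proportional-odds fits on the outcome grouped into at most 10 categories (means of 4 replicates). The comparison sites had fewer 30-day patients, moved equally to 90 and 180 days.

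| Fewer on 30 d | OR, same delay at every interval | OR, delay scales with interval |
|---|---|---|
| 10 points | 1.20–1.21 | 1.10 |
| 20 points | 1.31–1.48 | 1.32 |
| 30 points | 1.54–1.85 | 1.49 |

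Adding interval as a covariate brought every OR to 0.97–1.04. With no difference in mix, the unadjusted OR was 0.98–1.04, which shows the simulation noise. On the SD scale the spurious differences were 0.02 to 0.27. Analysed as independent, 8,000 against 8,000 detects 2.80×√(2/8,000) = 0.044 SD at 80% power, so most of this range would be declared significant.

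**With full site terms.** An intercept, one intervention and three site indicators make five columns of rank 4. Site then absorbs the mix and the training effect together.

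**The case against.** Several points on the other side stand.

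- A reader might infer that interval has been excluded. The documents do not support that: the CPM covariates are examples, so the list is open, and prior pick-up history in the longer list is a plausible partial proxy. But that list belongs to the mixed models, and Appendix 9 does not clearly supply prior pick-ups for the full cohort. The accurate statement is that interval is not named.
- A reader might infer that the mix passes directly into the primary training estimate. As written, the primary CPM contains fixed site effects. If that set is full, the problem is that training and site cannot be separated, which an interval covariate does not repair. The direct route needs a model without full site terms, and there every other site difference enters too. The protocol already declares the four-site limitation.
- A reader might take 1.8 points as the size. It comes from the most pessimistic scenario; milder ones give 0.2 to 0.7, and less if delay scales with interval. The SD-scale range of 0.02 to 0.27 lies below the planned 0.64.
- The dependence is not purely a scoring artefact. Someone late six times does spend more days without a new supply than someone late once. Interval is better described as a strong prognostic covariate that may differ by site.

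None of this removes the dependence of the outcome on interval, which follows from the definition.

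**Conclusion.** The point holds as a covariate omission worth correcting before the primary model is fixed. The outcome depends on dispensing interval by construction, and no Objective 2 list commits to adjusting for it. The number of scheduled dates (6, 3, 2, 1) needs no lateness assumption. The size does: 0.2 to 1.8 percentage points of site mean per 10-point shift from 30- to 180-day supply, if lateness per pick-up is the same at every interval. Unadjusted odds ratios of about 1.1 to 1.85 for mix differences of 10 to 30 points apply only to models without site terms and rest on an assumed reference mix. The direction is unknown, because the actual mix and lateness are not in the documents.

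The documents do not support a claim that the trial's primary estimate is biased by a known amount, or that this adjustment would make the training effect identifiable alongside a full set of site terms.

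**What to change.** Pre-specify in the CPM a categorical covariate for the dispensing interval in force at the start of the 6-month window (30/60/90/180 days). Use the starting value only, since later changes could follow from the training. Use the same covariate in the interaction model, and report the dispensing mix by site.

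The cost is one covariate plus a short look-back extraction from the same electronic patient tracking system: the last pick-up and its scheduled next date before the window. The look-back is needed because Appendix 9 covers only the study period, and a six-month supply may have been dispensed earlier. The sponsor should also confirm how the dispensation-type field maps to the four intervals.

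A sensitivity analysis limited to patients with at least one scheduled date in the window is not worth adding. With intervals of at most 180 days it excludes essentially nobody (100% of simulated patients had such a date). The aliasing of training with site must be resolved separately.
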